Study Design	
Cohort A will be 34-weeks duration, and will be double-blinded, randomized, and placebo-controlled. Twenty subjects will be enrolled; 10 subjects per arm will receive either namilumab or placebo. All subjects will also be treated with prednisone 25-60 mg/day, or equivalent, in addition to other immunosuppressive therapy (IST) they may already be receiving. The Investigator will determine the starting dose of OCS. Subjects will be treated with prednisone at a dose ranging between 25-60 mg/day, or equivalent. Subjects should begin OCS treatment any time after the completion of the screening PET scan through completion of the Baseline Visit. Note the timing requirement for the OCS and PET scan pertains to the intended study dose of OCS (25-60 mg/day of prednisone or equivalent) and not to any pre-existing treatment of <math>\leq</math>10 mg/day of prednisone or equivalent. Subjects must agree to taper OCS over 22 weeks after randomization.
 
Cohort B is 34 weeks in duration, open-label, and with a single arm. Ten subjects will be enrolled. Eligible subjects for Cohort B are those who otherwise qualify for Cohort A but prefer not to receive high-dose OCS, or, in the opinion of the Investigator, are not suitable candidates to take prednisone 25-60 mg/day. The reason for not providing high-dose OCS should be documented in the subject's chart and source records. Subjects will receive open-label namilumab in addition to their background therapy without change to any ongoing OCS dose (<math>\leq</math>10 mg/day of prednisone or equivalent) or IST medication(s) and dose(s).

Study Treatments	
Cohort A:
 

• Treatment Arm 1: Namilumab administered subcutaneously (SC): 150 mg on Day 1, Day 15 (Week 2), and then every 4 weeks (Q4W) thereafter through Week 30.

• Treatment Arm 2: Placebo administered to match namilumab dosing.

 
Subjects randomized to Treatment Arm 1 or 2 will also be treated with prednisone 25-60 mg/day, or equivalent, in addition to any other background IST they are already receiving.
 
Cohort B:
 

• Namilumab administered SC: 150 mg on Day 1, Day 15 (Week 2), and then Q4W thereafter through Week 30.

 
Subjects enrolled in Cohort B must continue their background therapy without change to any ongoing OCS dose (<math>\leq 10</math> mg/day of prednisone or equivalent) or ISTs.

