## **3.2. Discussion of Study Design, Including the Choice of Control Group**

This study is an exploratory trial evaluating safety and tolerability of namilumab compared to placebo and in an open-label cohort in subjects with active CS. A robust, double-blind, randomized, placebo-controlled design has been selected for Cohort A. Such a design will provide strong evidence concerning the use of GM-CSF inhibition for the treatment of CS in addition to standard of care high dose OCS. It has been designed to closely match the standard of care for many CS subjects who would be typically treated with high dose OCS, then followed using [18-F] FDG-PET/CT scanning for response. Cohort B is designed to assess subjects who only receive open label namilumab in addition to their background OCS and/or IST. It has been designed to closely match the standard of care for those who are ineligible for, or who prefer not to receive high dose OCS. Although not placebo controlled, this cohort will provide evidence of the activity of namilumab in CS when used alone in addition to stable background therapy.

The trial is designed overall to provide strong evidence of safety and tolerability and preliminary evidence of the efficacy of namilumab in CS subjects and provide the evidence to support the further development of namilumab in this disease.

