## 6.4. Rescue Therapy

The clinical status of a subject in either Cohort may deteriorate. The Investigator should instruct subjects to contact study staff immediately if they feel their symptoms or signs of sarcoidosis, particularly of their cardiac disease, are worsening.

The Investigator may assess that the clinical deterioration is due to progression of CS and may wish to provide rescue therapy. In this circumstance, increased OCS dosing at the lowest effective increment with the shortest duration is the preferred option so that integrity of the study may be preserved. Alternatively, the change in regimen may be increased dosing of a current IST or the addition of a new one.

In this protocol rescue therapy is defined as any of the following:

- (Cohort A) Failure of the OCS taper, i.e., the subject requires an increase in OCS dose during the protocol-specified taper ([Appendix 8](#));
- (Cohort A) Protocol-specified dose levels cannot be reached by the pre-specified timepoints ([Appendix 8](#));
- (Cohort A) Increase in OCS dose above 10 mg/day prednisone, or equivalent, after the taper is complete;
- (Cohort B) Increase in OCS dose above 10 mg/day prednisone, or equivalent, at any time;
- (Either Cohort) Start of a new IST or change in dose or frequency of a current IST;
- (Either Cohort) Use of a prohibited medication to treat sarcoidosis-related signs or symptoms.

The following do not constitute rescue therapy:

- Use of OCS for up to 14 days or less for treatment of an event not related to sarcoidosis, e.g., an acute allergic reaction, acute contact dermatitis;
- Use of inhaled OCS or bronchodilators, e.g., long-acting beta agonists or long-acting muscarinic agonists.

Prior to initiating rescue therapy in a subject who is not hospitalized, an unscheduled visit should be performed; see [Sections 3.1.4](#) and [3.1.4.1](#) for details.

If it would not adversely affect a subject's safety or wellbeing, PET/CT and TTE should be performed before initiation of rescue therapy.

Cohort A subjects should resume the protocol-specified steroid taper ([Appendix 8](#)) at the earliest opportunity based on the Investigator's clinical judgement.

The Medical Monitor must be contacted if rescue therapy is initiated, and the reason(s) should be captured in source records and in the CRF.

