#### **Weeks 22-34**

Following the Week 22 Visit, subjects will receive 10 mg or less of prednisone daily (or its equivalent); based on the opinion of the Investigator. Further dose reduction below 10 mg of prednisone daily or its equivalent is encouraged if the clinical situation allows but is not required.

If a subject substantially deteriorates during the taper period in the opinion of the Investigator, then a "rescue" may be performed (see [Section 3.1.4.1](#)). In this scenario, the steroid dose may be maintained or increased back to a prior level, and the subject is considered to have failed the steroid taper. Steroid taper may be recommenced after assessing clinical response to rescue based on clinical judgement.

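### In Cohort B a steroid increase counts as rescue only above 10 mg/day, so a smaller increase given for worsening cardiac sarcoidosis is scored as no rescue

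*Combined protocol and SAP*

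**What the plan says.** Section 6.4 introduces its list with "In this protocol rescue therapy is defined as any of the following". The one OCS item for Cohort B is "Cohort B) Increase in OCS dose above 10 mg/day prednisone, or equivalent, at any time". It sets an absolute level and makes no reference to the dose on which the subject entered. Immunosuppressive therapy (IST) is treated differently, because every change counts: "Either Cohort) Start of a new IST or change in dose or frequency of a current IST".

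The text above the list covers deterioration that the investigator attributes to cardiac sarcoidosis. It says that "increased OCS dosing at the lowest effective increment with the shortest duration is the preferred option", and then: "Alternatively, the change in regimen may be increased dosing of a current IST or the addition of a new one".

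Other parts of the protocol bear on this:

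- Inclusion criterion 6 (Section 4.1) makes OCS optional at entry and caps it at 10 mg/day, stable for at least 4 weeks before the screening PET scan.
- The Synopsis (Study Treatments) states: "Subjects enrolled in Cohort B must continue their background therapy without change to any ongoing OCS dose". Section 3.1.1 repeats the rule.
- Section 3.2 says of Cohort B that "this cohort will provide evidence of the activity of namilumab in CS when used alone in addition to stable background therapy".
- Section 2.2 lists the proportion of subjects requiring rescue as a secondary endpoint for both cohorts.
- For Cohort A, Section 6.4 counts any OCS increase during the taper, but after the taper only one above 10 mg/day. Appendix 8 says of Weeks 22-34: "Further dose reduction below 10 mg of prednisone daily or its equivalent is encouraged", where the clinical situation allows.

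**The concern.** The endpoint definition is looser than the background rule on which Cohort B rests. A subject on 0 or 5 mg/day who is raised to 10 mg/day because the disease worsened has left the background regimen and has received the kind of treatment that Section 6.4 prefers as rescue. The list nevertheless scores no event. The rise needed to count depends on entry dose: any rise for a subject entering at 10 mg/day, but more than 10 mg/day for a subject entering on none.

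Two things are at stake. The first is the meaning of a named secondary endpoint in a cohort of 10. The second is the reading of Cohort B, which has no comparator and is described as showing namilumab activity over unchanged therapy. A reader of its PET results needs to know who had prednisone added.

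**Working it through.** The protocol gives no figure to reproduce here. The check applies the Section 6.4 rule to the entry doses that Section 4.1 allows.

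**Inputs.** Rescue threshold for Cohort B: above 10 mg/day (Section 6.4). Entry dose s: 0 to 10 mg/day (Section 4.1). Cohort B size: 10, single arm (Section 3.1). Treatment Period: 238 days (Section 3.1).

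**Step 1: which increases count.** Rescue requires a new dose above 10 mg/day, so the rise must exceed 10 − s. A new dose of exactly 10 mg/day is not above 10. The ceiling on uncounted added prednisone is (10 − s) × 238 days.

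| Entry dose (mg/day) | Rise needed to count (mg/day) | Raised to 10 mg/day: counted? | Ceiling on uncounted prednisone (mg) |
|---|---|---|---|
| 0 | more than 10 | no | 10 × 238 = 2,380 |
| 2.5 | more than 7.5 | no | 7.5 × 238 = 1,785 |
| 5 | more than 5 | no | 5 × 238 = 1,190 |
| 7.5 | more than 2.5 | no | 2.5 × 238 = 595 |
| 10 | any | no rise | 0 |

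The last column is an arithmetical limit, not an expected exposure. If the threshold were read as the size of the increment, the gap would be wider.

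**Step 2: does another item catch it?** The taper items apply to Cohort A only. OCS is not among the prohibited medications in Section 6.2. The IST item does not reach it either, because Section 6.4 offers an IST change as the alternative to an OCS increase. The Synopsis speaks of other IST beside prednisone, which hints that OCS might itself be an IST, but Sections 3.2, 6.2 and 6.4 keep the two apart.

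**Step 3: effect on the rescue proportion.** Each missed subject moves it by 1/10 = 10 percentage points. The exact (Clopper-Pearson) 95% limits are the 0.025 quantile of Beta(x, 10 − x + 1) and the 0.975 quantile of Beta(x + 1, 10 − x). The lower limit is 0 when x = 0.

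- 0/10: 0% (0 to 30.8)
- 1/10: 10% (0.3 to 44.5)
- 2/10: 20% (2.5 to 55.6)
- 3/10: 30% (6.7 to 65.2)

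**Step 4: how likely is at least one case?** The documents give no rate. If a share q of subjects has such an increase (assumption), the chance of at least one among 10 is 1 − (1 − q)^10. For q = 5%, 10%, 20% and 30% this gives 40%, 65%, 89% and 97%.

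**Step 5: does the label change the PET mean?** Efficacy analyses use the mITT population (Section 8.2.2), which is not defined by rescue status. Missing data are not imputed (Section 8.4). No section censors or excludes rescued subjects. A Cohort B subject raised to 10 mg/day and one raised above it enter the Week 34 mean change in the same way, so relabelling the first leaves the mean unchanged. What is absent is any mark that identifies the first.

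**Step 6: what else hangs on the label?** The Rescue Visit (Section 3.1.4.1), PET/CT and echocardiography before rescue, and contact with the Medical Monitor (both Section 6.4) are all tied to rescue. An increase that stays at or below 10 mg/day need not trigger any of them.

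**The case against.** The strongest reply is that the threshold is coherent and the information is not lost. The 10 mg/day level is the entry ceiling, the taper target and the upper end of the regimen after Week 22, so one cut-off serves both cohorts. For a subject already on OCS, an increase departs from the no-change rule and could, if judged a major violation, remove the subject from the Per-Protocol sensitivity set (Section 8.2.3). The dose is recorded daily in the eDiary (Section 5.5.2) and at visits (Appendix 1, footnote k), and it enters cumulative oral steroid use, itself a secondary endpoint. The study is Phase 2a with a safety primary endpoint and no efficacy hypothesis testing. Analysis detail is deferred to the SAP (Sections 8.4 and 8.5.1), and no SAP text on this point is present in the combined document.

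Much of this stands, and it limits what can be claimed. A reader might infer that the definition biases the Week 34 PET result; Step 5 shows that it does not. A reader might infer that the added steroid goes unseen; it is visible in the eDiary and in cumulative use. A reader might treat 2,380 mg as a realistic exposure; it assumes escalation on Day 1 held for all 238 days, which sits badly with the Section 6.4 preference for short courses. A reader might call a Cohort A return to 10 mg/day after Week 22 a miscounted rescue; Appendix 8 keeps that dose within the protocol regimen.

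The reply does not close the gap in the rescue endpoint. No passage explains why the absolute level was chosen over entry dose. What counts as a major violation is not defined, and the main efficacy set keeps the subject. The no-change wording in the Synopsis refers to an ongoing dose, so it does not clearly cover a new start from zero. Cumulative use shows how much prednisone was taken, not that an increase was given for worsening sarcoidosis.

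**Conclusion.** The point holds for the Cohort B rescue endpoint. As written, Section 6.4 scores an OCS increase to 10 mg/day or less for worsening cardiac sarcoidosis as no rescue. That does not match its own account of preferred rescue, its treatment of IST changes, or the rule that background OCS stays unchanged. Each such subject understates the Cohort B rescue proportion by 10 percentage points, assuming that all 10 planned subjects are in the denominator. The error can only run downward. The number affected is unknown: it depends on how many subjects enter below 10 mg/day and how many are escalated, and the documents give neither.

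The consequence for PET is one of interpretation. The Week 34 mean is unaffected by the label, but subjects with added prednisone cannot be separated from those on unchanged background, and the scan before escalation may not exist.

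**What to change.** 1. The sponsor should reconcile the Cohort B OCS item in Section 6.4 with the preferred-rescue text above it and with the no-change rule in the Synopsis and Section 3.1.1. The text should also settle whether a new OCS start from zero falls under that rule. Which dose rule applies is for the sponsor.
2. Keep the rescue endpoint as defined. Add to the SAP a supplementary count of Cohort B subjects with any OCS increase above entry dose given for sarcoidosis. Take the dose from the eDiary and the reason from the medication record (Section 6.1), and keep the existing exemption for courses of up to 14 days unrelated to sarcoidosis.
3. Flag these subjects in the Cohort B PET results, or show the results with and without them.
4. For Cohort A after the taper, report re-escalations for sarcoidosis descriptively only.

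The cost is one small tabulation and a flag. Dose and reason for use are already collected, though the record must give the reason for a change of dose as well as for the drug. The reported escalation rate may look less favourable. The change should be made before the SAP is signed, which Section 8.8 places before database lock.

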Namilumab has been studied in humans in doses ranging from 0.2 mg/kg to 8 mg/kg in Study M1 1188 001 EM; at 150 mg and 300 mg doses in Study M1 1188 002 EM (PRIORA) and Study MT 203 2004 (TELLUS); at 80 mg, 150 mg, and 300 mg in Study MT 203/CPH 001; at 20 mg, 80 mg, and 150 mg in Study M1 1188 202 (NEXUS); at 20 mg, 50 mg, 80 mg, 150 mg, and 300 mg in Study M1 1188 203 (NEPTUNE); at 150 mg in Study IZN 101 (NAMASTE); and at 150 mg in an Investigator-initiated trial (CATALYST). To date, 403 subjects or healthy volunteers have been enrolled into the clinical development program for namilumab, with 332 subjects estimated to have received namilumab. In addition, 57 subjects with COVID-19 were treated with a single dose of 150 mg namilumab in an Investigator-initiated trial in the UK known as the CATALYST study (n=55) or Investigator-sponsored compassionate use study (n=2). Overall, namilumab has been well tolerated with an acceptable safety profile for further development.

Based on the known data, the potential benefits of namilumab treatment outweigh the potential risks. Preclinical and human tissue studies have suggested that GM-CSF plays a key role in the formation of granulomas, including sarcoid granulomas. Positive clinical trials of anti-GM-CSF agents in RA, giant-cell arthritis, and COVID-19 have demonstrated a key role of GM-CSF as a driver of autoimmunity and hyperinflammation. The sarcoidosis subjects in this study will have relatively severe disease and may be receiving high doses of OCS or will have failed several agents. Current treatment strategies, including long-term use of OCS are associated with significant toxicities ([Khan, 2017](#)), and other treatment options for these subjects (cytotoxic agents and anti-TNF agents) have toxicity concerns of their own ([Callejas-Rubio et al, 2018](#)). Given that no new therapy has been approved for sarcoidosis in decades, namilumab may prove to be a useful treatment for these patients with limited options.

In summary, the anticipated potential risks include the occurrence of adverse reactions i.e., decreased neutrophil count/mild neutropenia, PAP, infection, and/or hypersensitivity reactions. No AEs suggestive of PAP, severe hypersensitivity, or severe neutropenia have been reported in the namilumab clinical program to date.

The following have been delineated as important identified risks:

- AST and/or ALT elevation.

The following have been delineated as important potential risks:

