- Decreased neutrophil count/mild neutropenia;
- PAP;
- Hypersensitivity/allergic reactions (IgE-mediated; non-IgE-mediated);
- Infection.

Based on nonclinical studies and the available data from 8 completed clinical studies, the risks associated with exposure to namilumab are justified by the anticipated benefits that may be afforded. The benefit-risk ratio for namilumab is considered positive for the further study of namilumab in subjects with CS.

Identified potential risks and the planned mitigation strategies are described in [Table 1](#). More detailed information about the known and expected benefits and risks, reasonably expected AEs associated with namilumab, and mitigation strategies may be found in the Investigator's Brochure.

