#### **Secondary Endpoints:**

- Other safety endpoints including:
  - Incidence and magnitude of treatment-emergent laboratory abnormalities;
  - Change from baseline in vital signs;
  - Change from baseline in ECG parameters.

- Mean change from baseline in PET maximum standardized update value (SUVmax), SUVmean, and total glycosylation;
- Cumulative arrhythmia burden and hospitalization for cardiac events;
- Mean change from baseline in left ventricular ejection fraction (LVEF) and global longitudinal strain (GLS) on transthoracic echocardiogram (TTE);
- Cumulative oral steroid use, modified glucocorticoid toxicity index (mGTI), and mean change from Baseline in glycosylated hemoglobin (HbA1C);
- Proportion of subjects requiring rescue therapy (either cohort) and proportion of subjects successfully achieving steroid taper without requiring rescue therapy (Cohort A);
- Mean change from baseline in KSQ (General and sub-domains), Fatigue Assessment Scale (FAS), and Subject Global Assessment (SGA);
- Assessments of PPK and E-R relationships for safety and efficacy if data permit.

**Note:** For endpoints defined as mean change from baseline, the primary assessment will be at Week 34.

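### Section 6.4 counts any change in dose or frequency of a current IST as rescue, so a reduction for toxicity is scored as rescue although the section describes only escalation

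*Combined protocol and SAP*

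**What the plan says.** Section 6.4 (Rescue Therapy) introduces its list with "In this protocol rescue therapy is defined as any of the following", so meeting one bullet is enough. The IST bullet is "Either Cohort) Start of a new IST or change in dose or frequency of a current IST".

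Earlier in the section, the setting is clinical deterioration that the investigator attributes to progression of cardiac sarcoidosis. An increase in oral corticosteroid (OCS) is preferred, and the IST option is described thus: "Alternatively, the change in regimen may be increased dosing of a current IST or the addition of a new one". The list of things that are not rescue has two items: OCS courses of up to 14 days for an event unrelated to sarcoidosis, and inhaled agents. No IST change is exempted.

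Once something is rescue, Section 6.4 asks for an unscheduled visit beforehand if the subject is not in hospital, and says that, where safe, "PET/CT and TTE should be performed before initiation of rescue therapy". The Medical Monitor must be told, and "the reason(s) should be captured in source records and in the CRF".

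Section 2.2 uses the term in two secondary endpoints: the proportion of subjects requiring rescue (either cohort) and the "proportion of subjects successfully achieving steroid taper without requiring rescue therapy (Cohort A").

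**The concern.** The definition is wider than the purpose that the section describes. Background IST is allowed in both cohorts, so a subject may need a lower or less frequent dose of, say, methotrexate because of raised transaminases or low counts. That is a change in dose or frequency, so under the list it is rescue. A tolerability event would then be read as lack of efficacy in the rescue proportion and possibly in the taper endpoint.

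The events that might prompt such a cut overlap with namilumab's own listed risks. Section 1.3 names "AST and/or ALT elevation" as the important identified risk, and among the important potential risks are "Decreased neutrophil count/mild neutropenia" and infection. Misclassification therefore need not fall equally on the two arms of Cohort A, and Cohort B has no comparator that would reveal it. With about 20 sites for about 30 subjects, one site may also follow the list while another follows the text above it.

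**Working it through.** **Textual check.** The protocol states no figure that depends on this point, so the first step is to compare the parts of Section 6.4.

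- *OCS, Cohort A after the taper and Cohort B at any time:* a direction is stated (an increase above 10 mg/day of prednisone or equivalent).
- *Prohibited medication:* an indication is stated (treating signs or symptoms of sarcoidosis).
- *IST:* a new agent, or any change in dose or frequency. Neither direction nor indication is stated.
- *Exemptions:* OCS given for an unrelated event is carved out. There is no counterpart for IST.
- *Narrative above the list:* only escalation or addition of IST is described, in permissive wording that does not limit the list.

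A reduction in dose or frequency therefore satisfies the IST bullet as written.

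**Which endpoints it reaches.** The rescue proportion is affected whenever the reduction occurs. The Cohort A taper endpoint is affected if the reduction falls within the 22 weeks of taper. Such a subject misses the rescue-free composite without meeting the separate bullet on failure of the OCS taper.

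**Size per subject.** Each Cohort A arm and Cohort B has 10 subjects (Synopsis, Study Design), so one reclassified subject moves the proportion by 1/10 = 10 percentage points. As an example with exact (Clopper-Pearson) 95% intervals: 0/10 is 0% (0 to 30.8%), and 1/10 is 10% (0.3 to 44.5%).

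**How often (assumed).** The documents give neither the share of subjects on IST nor a reduction rate. With k users in a group of 10 and a chance p of reduction for each, P(at least one) = 1 − (1 − p)^k:

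- k = 3, p = 0.05: 1 − 0.95^3 = 14.3%
- k = 5, p = 0.10: 1 − 0.90^5 = 41.0%
- k = 8, p = 0.15: 1 − 0.85^8 = 72.8%

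Assuming 0 to 2 cases per group, the shift is 0 to 20 points.

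**Between-arm illustration (assumed counts).** Suppose true rescue is 2/10 on namilumab and 4/10 on placebo. The difference is 20% − 40% = −20 points (Newcombe 95% CI −52.1 to +18.7). If one further namilumab subject is scored as rescued only because of an IST reduction, the difference is 30% − 40% = −10 points (−44.6 to +28.2). The estimate halves, and both intervals are wide and include zero.

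**Procedural effect.** Taken literally, the bullet would also call for a pre-rescue PET/CT where safe. Splitting the 22.2 to 41.7 mSv for up to three scans (Section 7.1.2.1) equally gives 22.2/3 = 7.4 to 41.7/3 = 13.9 mSv. This applies only if a site performs a scan that was evidently not meant.

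**The case against.** The best reply is that context already narrows the bullet. The section starts from progression, the endpoint speaks of subjects who require rescue, the Rescue Visit (Section 3.1.4.1) is there to confirm the need, and Appendix 8 ties rescue to substantial deterioration. This is strong evidence that escalation was intended. It does not cure the list, which is the stated definition and does not refer back to that context.

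A second reply is that such cases can be found before database lock. The Medical Monitor is contacted, the reason is recorded, and Section 6.1 collects dose, frequency, dates and reason for use. That is correct and limits the harm, but no rule is given for reclassifying a case once found. Sections 8.4 and 8.5.1 leave details to a SAP whose text is not in the document. It may narrow the derivation, and whether the final endpoint would miscount cannot be settled here.

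One might defend the bullet as a deliberate rule of stable background therapy, since Cohort B is to continue IST unchanged. But OCS reductions are not rescue, and in Cohort A reduction below 10 mg is encouraged, so a rule that penalises only IST reductions would be hard to justify.

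Three stronger readings are not supported:

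- *Every IST reduction in Cohort A fails the taper endpoint.* One made after Week 22 need not.
- *The definition biases the trial against namilumab.* Nothing in the documents says that namilumab leads to cuts in background IST. The liver actions in Section 4.4.2.4 and Appendix 7 are stopping study drug or continuing with weekly monitoring. Section 1.3 describes the white-cell decrease in the first-in-human study as not clinically significant and cites no increased infection risk in trials of this drug class. An imbalance is possible, not shown.
- *Interruptions and stops plainly count.* The bullet names dose and frequency only. Their status is unclear, which is a reason to state it.

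**Conclusion.** The point holds as an inconsistency between definition and intent that should be corrected. As written, a reduction in dose or frequency of a current IST for toxicity is rescue in either cohort and, during the taper, denies a Cohort A subject a rescue-free taper. The only firm figure is 10 percentage points per subject in a group of 10. The 14 to 73% chance of at least one case, the 0 to 20 point range and the halved difference rest on assumed rates and counts, and the true number may be zero.

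A reader might infer that a test or an error rate is at risk. It is not: Section 8.5 plans no hypothesis testing, nominal p-values are descriptive, and the primary endpoint is safety. What is affected is the point estimates of two secondary endpoints and how they are read.

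**What to change.** Reword the IST bullet as: *Start of a new IST, or increase in dose or frequency of a current IST, to treat sarcoidosis.*

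Add to the list of what is not rescue: *Reduction, interruption or stopping of an IST for toxicity or intolerance, and its later resumption at up to the Day 1 dose once the toxicity has resolved, provided the resumption is not given for worsening sarcoidosis.* The final condition matters. Without it, a subject whose IST was cut for toxicity, and who then flared and was re-escalated to the Day 1 dose, would escape being counted, and a real failure would be hidden.

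List these IST changes separately by treatment group with the reason, using the concomitant-medication data of Section 6.1 and keeping the reason entry that Section 6.4 requires. Carry the same rule into the SAP derivation.

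The cost is one reworded bullet, one added exemption and one extra listing. No assessments are added and permitted treatment does not change. There are two small downsides: a reduction still alters background therapy, which is why it should remain visible, and the investigator must judge the reason for each IST change.
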